### 7.3. Providers:

Dentists'/pediatric residents' preferences for the 2 treatment options and time needed to complete a baseline visit will be recorded for each of the 2 interventions and logged on the respective *CRF Intervention Visit* (Appendix 10, CRF 02 & 03).

Provider preference of treatment modality cannot be collected through the clinical measurements on the study Case Report Forms. Therefore, collecting this data from the provider in addition to the clinical measurements will show feasibility and likelihood of future use. It would also be of great interest to the dental community.

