## **2. Objectives**

The objectives of this clinical study are to evaluate:

- The effectiveness of treatment of cavitated caries in children by application of silver diamine fluoride (SDF) in comparison to conventional restorative treatments
- The perceptions of parents and patients to both treatment modalities and their levels of acceptability
- The opinions of dental providers in terms of ease of use and clinical time spent
- The relative cost-effectiveness of the two treatment approaches regarding both practitioner chair time and material-based cost

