## **4. Materials and Methods**

### **4.1. Purpose**

To determine the effectiveness of the application of silver diamine fluoride (SDF) in comparison to conventional restorative treatments in International Caries Detection and Assessment System criteria (ICDAS) 5 and 6, one and two surface carious lesions in primary molars which will be assessed based on major and minor failure criteria when followed for one year. Additionally, parents'/children's and providers' perceptions will be assessed as well as the cost of both regimens, to include both chair time spent and materials' costs.

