#### **4.3. Inclusion and Exclusion Criteria**

Eligible children will be identified during a screening at initial presentation. They must fulfill the inclusion criteria which include (Appendix 10, CRF 10):

- Patients must be ages 2-10.
- Presence of at least one active (soft) cavitated carious lesions in the primary dentition, extending into dentin (ICDAS 5 or 6) – Only one tooth will be selected for the study. All others will be restored and monitored according to the American Academy of Pediatric Dentistry (AAPD) guidelines.
- The selected tooth must have a one or two surface lesion (more than 1/3 of the crown of the tooth must be remaining) and must allow for direct application of SDF.
- Study teeth will not have any spontaneous or elicited pain due to caries, tooth mobility, or signs of pulpal infection.
- Selected primary teeth must have an anticipated exfoliation date greater than 12 months away.

Exclusion criteria include children with:

- Hereditary developmental defects such as Amelogenesis Imperfecta and Dentinogenesis Imperfecta
- Severe medical conditions that do not allow the child to be managed in the MCHC/UMSOD clinics
- Known allergy /sensitivity to dental materials being used, including SDF

- Inability of the child to cooperate for treatment, recall examinations, or periapical radiographs.
- Wards of the State, for consenting reasons

After approaching the parent with a brief discussion of the study, determining interest and asking brief pre-screening eligibility questions as approved by the Institutional Review Board (IRB), the informed consent process will occur. Parents will provide both written and verbal consent, and written and verbal assent will also be asked of the children older than age 8 (Appendices 2 &3). Following the informed consent process, full study eligibility criteria will be reviewed with the pediatric dental resident performing the procedure. At time of consent, the parent will also be provided the *Enrollment Information Form* (Appendix 4) as a reminder of important information and frequently asked questions. This form will include information regarding study purpose, duration (12 months, including application/restorative appointment, 3 follow-up visits, and additional follow-up phone calls/contacts), possible resulting appearance, and overall study protocol.

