Children who are enrolled to participate in the study will receive a full mouth caries examination using the ICDAS criteria (Examiners will be trained and calibrated in the ICDAS criteria prior to study initiation.), and will be randomly divided into two groups:

1. **Conventional management of caries group:** This group will receive traditional restorative care for one tooth with a one or two surface lesion – including composite, amalgam, or glass-ionomer restorations according to the current AAPD treatment guidelines.
2. **SDF management of caries group:** This group will receive applications of SDF applied to their carious lesion, in lieu of restoration placement, with the goal of “arresting caries”.

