## 6. Study Visits and Intermediate Contacts

Recalls for both groups will occur via phone questionnaire as well as follow-up visits. Participants will be contacted at 1 month, 2 months, 4.5 months and 9 months ( $\pm$  2 weeks) following restoration placement or application of SDF. Subjects will need to present to the clinic for follow-up visits at 3 months ( $\pm$  6 weeks), 6 months ( $\pm$  6 weeks), and for study completion at 12 months ( $\pm$  6 weeks) (Table 1). Subjects will also be called to schedule and confirm these follow-up visits; these short calls will require no payment to the study subjects. In the case of an emergency, an emergency visit will be scheduled at Mott Children's Health Center or the University of Michigan School of Dentistry. An emergency will be evaluated and treated according to the AAPD guidelines, followed by completion of appropriate case report forms (CRFs) and reporting to IRBs and study sponsors (Appendix 10, CRF 14-17). In the event of minor or major failure in either study group, the subject will be withdrawn from the study and teeth will be given the appropriate treatment as stated in the AAPD Guidelines free of charge, these teeth will be categorized as a failure, and a *CRF 04 Treatment Deviation CRF (Appendix 10, CRF 04)* will be completed.

**Table 1.** Patient Contact Interval

Patient Contact	Recall Interaction	Time Scale
Clinic Visit #1	Consent/Accent, baseline questionnaires, initial caries assessment, radiographs*, intervention	T = 0
Intermediate Contact	Attrition prevention, update contact information, follow-up on pain	T = 1 month, 2 months (Additional reminder for Clinical Visit #2)
Clinic Visit #2	Assessment for major and minor failure & assessment of pain and parent satisfaction	T = 3 months
Intermediate Contact	Attrition prevention, update contact information, follow-up on pain	T = 4.5 months (Additional call reminder for Clinical Visit #3)
Clinic Visit #3	Reapplication of SDF in that group; Assessment for major & minor failure, radiographs*, and assessment of pain and parent satisfaction	T = 6 months

Intermediate Contact	Attrition prevention, update contact information, follow-up on pain	T = 9 months (Additional call for scheduling/reminder for Clinical Visit #4)
Clinic Visit #4	Assessment for major & minor failure, radiographs*, and final questionnaires	T = 12 months

\* Radiographs will be obtained only if an existing radiograph within 30 days of the visit is not available.

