### 7.2. Clinical Variables

At the baseline visit the study teeth carious lesions will be assessed based on size (mm), dentin color (yellow, brown, black), dentin hardness (soft - any explorer penetration of dentin when very light force is applied or hard – no dentin penetration when using an explorer with very light force), and periapical radiographs (outer/middle/inner third of dentin, major/minor failure criteria). All information will be noted on the respective *CRF Intervention Visit* by the provider prior to treatment. These clinical characteristics will also be recorded for the SDF groups at follow-up visits (as the lesion is exposed clinically). Recall clinical visits will involve assessment of the lesion based on minor and major failure criteria (Table 2). All assessments will be noted on the respective *CRF 3 & 6 Month* (Appendix 10, CRF 10 & 11) or on the *CRF 12 Month* at the patient's 12 month recall (Appendix 10, CRF 12 & 13). Both groups will have periapical radiographs taken at the baseline and 6 and 12 month recalls (and at any other time if deemed clinically necessary). If a radiograph from within 30 days of the visit is available, a radiograph will not be taken at the study visit unless deemed clinically necessary. De-identified clinical photos will also be taken as deemed necessary for research and publication purposes, with parental consent. Length of time and cost for each intervention will be calculated and analyzed for comparison.

**Table 2.** Major and Minor Failure Criteria

	SDF Application	Conventional Restoration
Success	
 
• Caries arrested – dentin feels hard to explorer
 
• No clinical signs or symptoms of pulpal pathology
 
• Tooth exfoliated without major or minor failure
 
	
 
• Restoration appears satisfactory
 
• No clinical signs or symptoms of pulpal pathology
 
• Tooth exfoliated without major or minor failure
 

Minor Failure	
 
• Caries progression – soft dentin, increase in lesion size clinically or radiographically
 
• Reversible pulpitis to be treated without pulpotomy or extraction
 
	
 
• Secondary caries
 
• Restoration fracture or wear requiring repair
 
• Loss of restoration
 
• Reversible pulpitis to be treated without pulpotomy or extraction
 

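### Section 7.3 records the time for the whole baseline visit, while the objectives and Section 7.2 promise chair time and the time for each intervention; the timed interval needs defining

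*Combined protocol and SAP*

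**What the plan says.** The sections describe the time outcome differently.

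- **Section 2 (Objectives)** plans a cost-effectiveness comparison "regarding both practitioner chair time and material-based cost". A separate objective covers provider opinion on clinical time spent.
- **Section 4.1 (Purpose)** describes the cost of both regimens as "to include both chair time spent and materials' costs".
- **Section 7.2 (Clinical Variables)** says: "Length of time and cost for each intervention will be calculated and analyzed for comparison".
- **Section 7.3 (Providers)**, the only place that says what is written down, states that "time needed to complete a baseline visit will be recorded for each of the 2 interventions", logged on the intervention-visit forms CRF 02 and CRF 03.
- **Section 7.4 (Economic Measures)** bases the evaluation on time and material cost without defining time further.

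Table 1 in Section 6 lists the content of Clinic Visit #1 as "Consent/Accent, baseline questionnaires, initial caries assessment, radiographs*, intervention". Its footnote adds: "Radiographs will be obtained only if an existing radiograph within 30 days of the visit is not available". Section 4.3 also says that enrolled children "will receive a full mouth caries examination using the ICDAS criteria". On carious teeth other than the study tooth, the same section says: "All others will be restored and monitored according to the American Academy of Pediatric Dentistry (AAPD) guidelines". It does not say at which visit.

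**The concern.** The quantity recorded (a visit) is wider than the quantity promised (an intervention, or chair time). Consent and questionnaires are research tasks that would not occur in routine care. Caries assessment is common to both arms. Radiographs are taken for some children and not for others. None of these distinguishes SDF from a restoration.

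Time feeds two of the four objectives: the provider's view of ease and time, and relative cost-effectiveness. SDF, as described in Section 5.2, involves no caries removal, so it may be a short procedure set inside a much longer visit. Recorded time could then consist mostly of tasks unrelated to the treatment. Section 11 has five or six residents at each of two sites doing the screening, treatment and recall. The training it describes covers colour, hardness and SDF technique, and does not mention timing. Without a definition, residents may time different intervals. If only visit time is kept, procedure time cannot be reliably recovered afterwards.

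**Working it through.** **Step 1. Is there a figure to reproduce?** No. The documents give no procedure time, standard deviation (SD) or expected time difference. The sample size in Section 4.2 concerns failure rates and does not bear on this point.

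**Step 2. What separates visit time from intervention time?** Write visit time as V = P + C. P is the study-tooth procedure. C is everything else in the visit: consent, questionnaires, examination, and radiographs if taken. Sections 2, 4.1 and 7.2 call for P, or for P plus a stated part of C. Section 7.3, read literally, records V. No section gives a start point, a stop point or a way of deriving P from V.

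**Step 3. Effect on the difference, the ratio and absolute time.** Assumed for illustration, not from the documents: P = 10 minutes for SDF and 35 minutes for a restoration, with C equal in both arms.

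| C (min) | SDF visit | Restoration visit | Difference | Ratio |
|---|---|---|---|---|
| 0 | 10 | 35 | 25 | 35/10 = 3.5 |
| 20 | 30 | 55 | 25 | 55/30 = 1.83 |
| 40 | 50 | 75 | 25 | 75/50 = 1.50 |
| 60 | 70 | 95 | 25 | 95/70 = 1.36 |

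The difference does not move, because C cancels: (35 + C) − (10 + C) = 25. Absolute time is overstated 3 to 7 times for SDF (30/10 to 70/10) and 1.6 to 2.7 times for restorations (55/35 to 95/35).

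A second assumed pair, 10 and 30 minutes, behaves the same way. With C of 15, 30 and 60 minutes the ratio falls from 3.0 to 45/25 = 1.8, 60/40 = 1.5 and 90/70 = 1.29, while the difference stays at 20 minutes.

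**Step 4. Effect on precision.** If C varies independently of P, SD(V) = √(SD(P)² + SD(C)²). With r = SD(C)/SD(P), the standardised difference is multiplied by 1/√(1 + r²), and the confidence interval for the mean difference is √(1 + r²) times as wide.

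| r (assumed) | Standardised difference retained | Interval width |
|---|---|---|
| 0.5 | 89% | 1.12 times |
| 1 | 71% | 1.41 times |
| 2 | 45% | 2.24 times |

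For example, SD(P) = 8 and SD(C) = 15 minutes give √(64 + 225) = 17.0, and 17.0/8 = 2.1 times as wide.

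**Step 5. Other teeth.** Section 4.3 says other carious teeth will be restored and applies this to every enrolled child, without naming the visit. If some of that work falls at Clinic Visit #1, its time enters V in both arms. With equal frequency in the two arms it acts like a larger and more variable C. The documents do not settle whether it happens at that visit.

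**The case against.** Several counter-arguments carry weight.

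- **The wording may simply be loose.** Section 7.3 ties the time to each intervention and logs it on the intervention-visit form, which Sections 5.1 and 5.2 have the provider complete after treatment. Section 8 calls the same visit the intervention appointment, and Section 7.2 names intervention time as what is compared. A reader might infer from 7.3 that chair time is not measured at all. The documents do not support that: they are inconsistent, and 7.2 states the right target.
- **The forms are not in the supplied text.** CRF 02, CRF 03 and the visit workflows (Appendices 5 to 8) may already hold procedure start and stop times. This stands. It is only partly reassuring, because Section 7.2 also has baseline lesion size, colour, hardness and radiographic findings entered on the intervention-visit form before treatment. Logging time there does not show that only the procedure is timed.
- **Common time does not bias the contrast.** This stands. Incremental cost uses the difference in means, so a smaller ratio does not show a distorted incremental cost.
- **Same-visit work on other teeth is an inference.** This also stands. A reader might go further and suppose that such work contaminates the SDF arm. For instance, 30% of SDF children and no controls having one extra 35-minute restoration would cut the 25-minute difference to 35 − (10 + 0.30 × 35) = 14.5. Nothing in the documents supports such a split or its direction. The rule covers all children, and allocation is randomised 1:1.
- **Examination and radiographs occupy the practitioner.** Whether they count as chair time is a legitimate costing choice. But that choice has to be stated, and consent and questionnaires would remain in the total.

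**Conclusion.** The point holds as a mismatch with practical consequences. The one stated recording rule names the baseline visit, and the outcome promised elsewhere is chair time or intervention time. Followed as written, the rule overstates absolute time cost in each arm, pulls the ratio towards 1 (from 3.5 to between 1.8 and 1.4 under the first set of assumed minutes) and widens the interval for the difference by an amount that depends on how variable the rest of the visit is.

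It does not follow that the comparison between arms is biased. The unchanged 25-minute difference rests on C having the same mean in both arms. Randomisation supports this as long as the assigned treatment does not alter how long the other tasks take. All minutes and SDs above are assumptions.

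The matter is worth correcting because absolute chair-time cost is an input to Section 7.4. It concerns secondary provider and economic outcomes only, and leaves the primary outcome and the sample size untouched.

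**What to change.** In Section 7.3, replace baseline-visit time with start and stop clock times for the study-tooth procedure only, entered on CRF 02 or CRF 03. Name the two end points. One option is to start at anaesthesia or isolation of the study tooth, whichever comes first, and stop at completion of that tooth. State whether set-up before isolation and the SDF drying period in Section 5.2 are counted. If the forms already contain such fields, align the wording of 7.3 with them.

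Exclude time spent on any other tooth at that visit, and note on the form that such work took place. Use the same definition in Sections 7.2 and 7.4. If examination and radiograph time is wanted in the economic evaluation, cost it as a separate item.

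The cost is two clock entries and a short note per child, plus a few minutes of provider training. Clinical care does not change.

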### 7.4. Economic Measures

The economic evaluation of the two treatment strategies will be based on the time and material-based cost which will be calculated with the assistance of a Masters of Public Health student.

Additionally, this study offers the potential opportunity for continued research in long-term recalls and histological analysis of the study teeth upon exfoliation.

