### **4.2. General Outline**

Children, 2-10 years of age will be invited to participate. The original study site is Mott Children's Health Center (MCHC) in Genesee County, Michigan. Following a slow recruitment period, the University of Michigan School of Dentistry (UMSOD) Children's Clinic was added as a second study site. Given the current data in the literature, the combined failure rate for conventional restorative techniques (e.g. compomers) is approximately 29% at one year follow-up, while application of silver diamine fluoride has a failure rate of 63% at one year follow-up, with increased success over time. Although the failure rate of SDF at one-year follow-up seems alarming, as indicated by Zhi, *et al.* it may be possible to increase the success rate with additional applications providing success rates up to 90.1% at 24 months. Using these data,  $\alpha$ -value of 0.05 and a Power set at 80%, the resulting sample size would be 68 (34 per group) as calculated using the software, nQuery (Appendix 1). To account for 30% attrition, the final number needed for the initial study will be 98 (92 for 25% attrition, 86 for 20% attrition). Subjects will be contacted by phone regularly and invited to two intermediate clinic visits (plus a final study visit) to reduce attrition (Table 1). Given a review of the current literature of the few Randomized Controlled Clinical Trials involving SDF worldwide, the majority of this research has been completed with pre-school aged children. Almost all research discusses arresting or prevention of caries in the

primary dentition, as well as prevention of caries on first permanent molars. Due to the strength of the current research, this study will be focused on the primary dentition of children in the U.S. These children and their parents will be approached when presenting for examination/recall/or treatment at Mott Children's Health Center, Flint, MI, or the University of Michigan School of Dentistry Children's Clinic, Ann Arbor, MI. Interested families with children that qualify following screening examination will be provided with an *Informed Consent/Assent* (Appendix 3) and an *Enrollment Information Form* (Appendix 4).

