### **5.2. SDF management of caries**

- The selected tooth with notable decay into dentin will be isolated with cotton rolls.
- No caries removal will be performed, except for food or other obvious debris.
- Tooth will be dried with gauze and SDF solution will be placed on the carious dentin until it is saturated.
- Excess SDF will be blotted dry with a cotton pellet.
- A second application of SDF solution will then be placed to ensure that the entire carious surface is wetted, and excess will again be blotted with a cotton pellet.
- Following the second application of SDF, the area will be isolated for 3 minutes to allow for ample drying before allowing contact with saliva and soft tissues
- Should the SDF come in contact with any soft tissues, soft tissue should immediately be wiped with a saline wipe
- Following completion of the SDF intervention visit, the provider will complete the CRF 03 *Intervention Visit: Silver Diamine Fluoride* CRF (Appendix 10, CRF 03).
- A second application of SDF will be applied at 6 month recall, following the same protocol as noted above (Due to the potential for increased caries arrest rate with a 6 month application).
- Any new carious lesions that develop after the initial treatment will be recorded, and treated using conventional treatment methods and will not be included in the study.
- Following the completion of this study, teeth in the SDF group will be treated according to AAPD guidelines or observed for exfoliation. The parent of an SDF treated child can elect a restoration following AAPD guidelines at the 12 month visit.

Both groups will receive the following, according the standard procedures at the MCHC/UMSOD:

- Oral Health Instruction (OHI) and diet instruction
- Tooth brushing/dentifrice use at home
- Fissure sealants for permanent teeth will be placed if deemed necessary.
- Traditional preventative care at recalls based on AAPD guidelines (Regular recall exams, prophylaxis, scaling, flossing, and fluoride varnish at 6 month recalls will be provided for both treatment arms. Special care will be taken to not apply fluoride varnish directly to the carious lesion which is being treated with SDF.)

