## **10. Statistical Analysis**

Power of the study will be fixed at 80% ( $\beta=0.20$ ) just as was used in calculation for necessary sample size, with  $\alpha = 0.05$  as the significance level. Data will be entered into SPSS Statistics or

another secured data collection system and data will be analyzed. Information will be stored on a password protected computer using an encrypted file and will be maintained as confidential protected health information (PHI). Examiners will be trained at the start of the study and calibrated on the use of the ICDAS criteria, and on the clinical outcome variables using extracted teeth to determine intra and inter-examiner reliability (dentin color, dentin hardness, and lesion size in mm), which will be measured with kappa statistics. A Chi-square test will be applied to determine if there is a difference in distribution of variables such as age, gender, brushing habits, fluoride exposure, etc. Chi-square tests will also be used to determine differences in dropout rates, failure rates, patient satisfaction/acceptance, and overall cost. The primary outcome, the proportion of children reporting major failures during the 12 month follow up period, will be analyzed using a mixed model with a binomial error structure. We will also analyze minor failures in a similar manner. The dependent variables will be a binary indicator of major failure, with differences between study treatments fitted as fixed effects. Estimates of the relative risk of major failure in the two groups will be presented in the form of odds ratios and associated 95% confidence intervals. Within this framework we will be able to estimate:

1. The mean difference between groups at the end of the follow up period;
2. The mean difference between groups across the whole of the follow up period; and
3. The difference in the rate of change of the outcome across the follow up period

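### The stated objective is relative cost-effectiveness, but the planned economic analysis compares cost alone and never joins it to treatment success

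*Combined protocol and SAP*

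**What the plan says.** The fourth objective in Section 2 is "The relative cost-effectiveness of the two treatment approaches regarding both practitioner chair time and material-based cost". The places that carry it out are these:

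- Section 4.1 (Purpose) restates the aim as "as well as the cost of both regimens, to include both chair time spent and materials' costs".
- Section 7.2 (Clinical Variables): "Length of time and cost for each intervention will be calculated and analyzed for comparison".
- Section 7.4 (Economic Measures): "The economic evaluation of the two treatment strategies will be based on the time and material-based cost". It names no effect measure.
- Section 10 (Statistical Analysis): "Chi-square tests will also be used to determine differences in dropout rates, failure rates, patient satisfaction/acceptance, and overall cost". Failure and cost are separate entries in that list.

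On resource use, Section 7.3 states that "time needed to complete a baseline visit will be recorded for each of the 2 interventions", while Section 5.2 states that "A second application of SDF will be applied at 6 month recall". Section 6 says that a child whose study tooth fails is withdrawn, counted as a failure and given further treatment. It does not say whether that treatment enters the cost.

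On outcome, Table 2 in Section 7.2 defines success, minor failure and major failure for the single study tooth of each child. Section 4.2 plans on 29% failure at one year for conventional treatment and states that "application of silver diamine fluoride has a failure rate of 63% at one year follow-up".

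**The concern.** Cost-effectiveness relates what is spent to what is gained. A comparison of cost alone settles the question only when outcomes are equal, or when the cheaper arm does at least as well. The planning assumption here is the reverse: the arm expected to be cheaper is also expected to fail more often. The question is then what each additional success costs, and no section defines a quantity that answers it.

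If the analysis is followed as written, the fourth objective is left without a result. A lower cost for SDF could then be described as better cost-effectiveness with nothing in the plan to test that description.

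**Working it through.** **Plan's own figures.** There is no economic figure to reproduce. The failure rates can be checked because the sample size rests on them. For 29% v 63%, two-sided alpha 0.05 (sidedness assumed), 80% power and pooled variance without continuity correction, the result is 33 per group, against 34 stated. With 34 per group, power is 81.8%. Inflating for 30% attrition, 34/0.70 = 48.6, rounded up to 49 per group, or 98 in total, as stated. The unequal outcomes are therefore the working assumption of the trial.

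**Inputs.**
- Conventional success: 1 − 0.29 = 0.71 (Section 4.2).
- SDF success: 1 − 0.63 = 0.37 (Section 4.2). Section 3.5 ties 37% arrest at 12 months to annual application.
- SDF success, alternative: 0.53, the 12-month arrest rate that Section 3.5 gives for biannual application. This is closer to the regimen here, which reapplies at 6 months.
- Cost ratio r = SDF cost / restoration cost per child. It is not in the documents and is varied below.

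**Average cost per success.** This is cost / success rate. SDF is lower when r < success(SDF)/success(conventional):
- biannual rate: 0.53/0.71 = 0.75
- planning rate: 0.37/0.71 = 0.52

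Between that value and r = 1, SDF is cheaper per child but dearer per success.

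**Incremental cost per additional success.** This is (conventional cost − SDF cost) / (conventional success − SDF success). The denominator is 0.71 − 0.53 = 0.18 or 0.71 − 0.37 = 0.34. With a restoration set at 100, conventional cost per success is 100/0.71 = 141:

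| SDF cost | SDF success | Cost per success, SDF v conventional | Cost of each extra success with conventional |
|---|---|---|---|
| 30 | 53% | 57 v 141 | 70/0.18 = 389 |
| 30 | 37% | 81 v 141 | 70/0.34 = 206 |
| 70 | 53% | 132 v 141 | 30/0.18 = 167 |
| 70 | 37% | 189 v 141 | 30/0.34 = 88 |
| 80 | 53% | 151 v 141 | 20/0.18 = 111 |
| 80 | 37% | 216 v 141 | 20/0.34 = 59 |

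Nothing switches in the last column at 0.52 or 0.75. Whenever SDF is cheaper and less effective there is a trade-off, and the ratio states its price.

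**What is counted also matters.**
- Suppose each SDF application costs 40, every child receives two, and success is 53%. Costing the baseline visit only gives 40/0.53 = 75 per success. Costing both gives 80/0.53 = 151, against 141 for conventional.
- Suppose each failure costs one further restoration. Total costs are then equal when r + (1 − success(SDF)) = 1 + 0.29, that is r = 0.82 at 53% or r = 0.66 at 37%.

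**Precision at 34 per arm.** The standard error of the success difference is √[(0.53×0.47 + 0.71×0.29)/34] = 0.116 at the biannual rate, so 0.18 ± 1.96×0.116 runs from about −0.05 to 0.41. At the planning rate it is √[(0.37×0.63 + 0.71×0.29)/34] = 0.114, so 0.34 ± 0.22 runs from about 0.12 to 0.56. In the first case the denominator of the ratio can cross zero.

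**The case against.** The strongest reply is that the authors intend only a cost comparison. The objective itself names chair time and materials, Section 4.1 speaks of cost, and Section 3.6 speaks of affordability. This is plausible, and it is why renaming the objective is an acceptable remedy. It does not remove the mismatch, because the objective as written promises more than the analysis delivers.

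Three stronger readings are tempting, and the documents do not support them.

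- A reader might infer that SDF will be reported as more cost-effective simply because it is cheap. No rule in the plan turns lower cost into that claim, and Section 10 lists failure rates beside cost. It is a possibility only.
- A reader might take 52% or 75% as the point where the conclusion reverses. Both are break-evens for average cost per success, not for an incremental ratio. No treatment costs are given, and the protocol describes SDF as inexpensive and quick (Sections 3.1 and 3.6), so the true cost ratio may lie below both. The 52% figure also rests on an arrest rate for annual application.
- A reader might conclude that the trial cannot answer the question at all. Outcomes are recorded for each study tooth, and time and cost are to be calculated for each intervention. What is missing is the measure that links them.

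It is also fair to say that a joint analysis may need more than new wording. Recorded time is specified for the baseline visit only, and the case report forms in Appendix 10 are not available to show whether more is captured.

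**Conclusion.** The mismatch between objective and analysis stands. Section 2 promises relative cost-effectiveness, Sections 4.1, 7.2, 7.4 and 10 provide cost alone, and Section 4.2 assumes the unequal outcomes under which cost alone is not enough. This affects a secondary objective and leaves the primary analysis untouched, but it should be corrected.

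Its size cannot be fixed from the documents. As an illustration, ranking by cost and ranking by average cost per success disagree for cost ratios from 0.75 to 1 at the biannual arrest rate, or from 0.52 to 1 at the planning rate. Below those values the two rankings agree, although the price of each extra success would still be unreported. The illustration assumes that the published arrest rates carry over to success as defined in Table 2, and that r covers the whole SDF regimen.

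**What to change.** In Sections 7.4 and 10:

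- Define the economic result as two differences reported together: mean cost per child, and the proportion of children whose study tooth is free of major or minor failure at 12 months.
- Add the incremental cost per additional success, with a joint bootstrap interval or an acceptability curve that resamples each child's cost and outcome as a pair. The curve is easier to read if the success difference may include zero.
- Replace the chi-square entry for overall cost with an estimated cost difference and its interval, since cost is not a categorical variable.
- Count the cost of the 6-month SDF reapplication, and state whether treatment after failure is counted in both arms.

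If only costs are to be compared, rename the fourth objective a cost comparison and draw no conclusion about cost-effectiveness.

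The cost is modest: revised wording, a little extra analysis, and logging time at the 6-month reapplication if the case report forms do not already do so. The interval will be wide at about 34 evaluable children per arm, and the report should say so.
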